## PREDISCHARGE

The patient will be assessed at pre-discharge for the occurrence of any major adverse events including: death, need for open heart surgery, cardiac tamponade, or need for re-operation.

## **STATISTICAL PLAN AND CONSIDERATIONS**

Using Stata statistical software (StataCorp LP, College Station, Texas), ILA grades will be correlated to the time required and amount of laser pulsations delivered to traverse each vascular segment. Spearman correlation coefficients will be calculated. The student's T-test will be used for continuous comparisons. Fisher's exact or the Chi-square test will be applied for dichotomous variables.

## **RISKS AND BENEFITS**

### RISKS

It is standard of care to insert 2 or more large (7F – 12F) venous sheaths in the right and left femoral veins during TLE. This is done to provide access for large volume resuscitation and a conduit for temporary peripheral bypass in the event of a major vascular complication like SVC or RV tear [4]. In many centers ICE is already being utilized during TLE to monitor for complications. This study will require the operator to manipulate the IVUS catheter in the RA, SVC and IV. Potential risks of the overall procedure include venous perforation leading to cardiac tamponade. Based on published data, the risk of this event occurring is very low [11-13]. Specifically, in a recent review of ICE/IVUS in EP procedures that was published in 2018, ICE/IVUS use was not associated with any major complications. Additionally, there were no adverse events seen with use of IVUS in our cohort of 56 patients that Drs. [name] and I studied. Please refer to IFU's for potential risks associated with IVUS catheter. [Appendix B] While we believe there are little to no added risks for using IVUS, procedure time may be increased by 10 minutes in order to capture images via IVUS. In our experience though, the acquisition of IVUS images can be done simultaneously with other parts of the procedure thereby not adding any additional time to the procedure.

## BENEFITS

IVUS shows promise as a tool to evaluate the presence of ILA in the SVC and other cardiac structures. This could potentially allow operators to risk-stratify the allowing them to better select the resources, tools and approach to the procedure.

## **SAFETY AND ADVERSE EVENTS**

### Monitoring of Adverse Events

During the procedure, participants will be monitored by physicians (including anesthesiology), nurses, and technicians in accordance with standard operating procedures for routine catheter ablation procedures. Real-time hemodynamic monitoring during the procedure will be measured using arterial access. Real-time cardiac visualization will occur with the use of intracardiac echocardiography.

Post-operative monitoring will follow standard care for clinical ablation procedures, which includes overnight admission for observation with monitored telemetry and measurement of heart rate, blood pressure, oxygen saturation, and respiratory rate.

*Table 1 Adverse Event Definitions and Grading*

Term	Definition
Adverse Event (AE) Ref: ISO 14155-2011	Any untoward medical occurrence, unintended disease or injury, or any untoward clinical signs (including an abnormal laboratory finding) in subjects, users or other persons, whether or not related to the investigational medical device.
Ref: MEDDEV 2.7/3 12/2010	This definition includes events related to the procedures involved (any procedure in the clinical investigation plan).
Adverse Device Effect (ADE) Ref: ISO 14155-2011 Ref: MEDDEV 2.7/3 12/2010	Adverse event related to the use of an investigational medical device  This definition includes any adverse event resulting from insufficient or inadequate instructions for use, the deployment, the implantation, the installation, the operation, or any malfunction of the investigational medical device.  This definition includes any event resulting from use error or from intentional misuse of the investigational medical device.
Serious Adverse Event (SAE) Ref: ISO 14155-2011 Ref: MEDDEV 2.7/3 12/2010	Adverse event that led to: 

• Death

• Serious deterioration in the health of the subject, that either resulted in:

○ a life-threatening illness or injury, or

Term	Definition
	
 
○ a permanent impairment of a body structure or a body function, or
 
○ in-patient or prolonged hospitalization of existing hospitalization, or
 
○ medical or surgical intervention to prevent life-threatening illness or injury or permanent impairment to a body structure or a body function
 
● Fetal distress, fetal death, or a congenital abnormality or birth defect.
 
 
NOTE: Planned hospitalization for a pre-existing condition, or a procedure required by the clinical investigational plan, without serious deterioration in health, is not considered a serious adverse event.

Serious Adverse Device Effect (SADE)
 
Ref: ISO 14155-2011
 
Ref: MEDDEV 2.7/3 12/2010
	
Adverse device effect that has resulted in any of the consequences characteristic of a serious adverse event.

Unanticipated Adverse Device Effect (UADE)
 
Ref: 21 CFR Part 812
	
Any serious adverse effect on health or safety or any life-threatening problem or death caused by, or associated with, a device, if that effect, problem, or death was not previously identified in nature, severity, or degree of incidence in the investigational plan or application (including a supplementary plan or application), or any other unanticipated serious problem associated with a device that relates to the rights, safety, or welfare of subjects.

Device Deficiency
 
Ref: ISO 14155-2011
 
Ref: MEDDEV 2.7/3 12/2010
	
A device deficiency is any inadequacy of a medical device with respect to its identity, quality, durability, reliability, safety or performance.
 
NOTE: Device deficiencies include malfunctions, misuse or use errors, and inadequate labeling.

Underlying diseases are not reported as AEs unless there is an increase in severity or frequency during the course of the investigation.

#### A. Assessing Relationship to Study Device

The site investigator will be responsible for assessing the relationship of the AE to the study device as related or unrelated, and for reporting the event to UChicago according to criteria in Appendix C.

*Table 2 Adverse Event Relatedness Criteria*

Classification	Description
Unrelated	The adverse event is determined to be due to a concurrent illness or effect of another device/drug and is not related to the investigational product.
Related	
 
• The adverse event is determined to be potentially related to the investigational product, and an alternative etiology is equally or less likely compared to the potential relationship to investigational product, or
 
• There is a strong relationship to investigational product, or recurs on re-challenge, and another etiology is unlikely, or
 
• There is no other reasonable medical explanation for the event.
 

## B. Adverse Event Reporting

Adverse events should be reported to the UChicago study team according to the table in Appendix C.

The site investigator is responsible for expeditiously evaluating adverse events for severity and causality designation according to details in Tables 1 and 2. The site investigator is responsible for providing supporting documentation to UChicago. All AEs that are considered related to the study or the device must be followed to resolution.

The UChicago study team will report adverse events to the FDA, UChicago IRB, and Phillips according to details in Appendix C.

All SAEs reported from participating sites will be reviewed by the Lead Principal Investigator or his/her physician designee. Only those determined to be serious and unexpected by the Lead Principal Investigator will be distributed to participating sites. If Phillips informs the Lead PI of new device information that impacts the safety of subjects, the UChicago study team will be responsible for distributing this information to sites.

A safety monitor (a physician who is not part of the study and does not perform TLE) will be designated. His/her role will be to evaluate and adjudicate any potential IVUS related adverse events. The study will be halted upon the discovery of unanticipated adverse device effects that present a significant or unreasonable risk to subjects enrolled in the study.

## **STUDY MONITORING, AUDITING AND INSPECTING**

The University of Chicago responsibility as the clinical sponsor is to ensure protocol and regulatory compliance through proper monitoring of the investigation. The University of Chicago requires IRB review and a subject Informed Consent Form for all research. Monitoring may be conducted remotely by The University of Chicago Research Office.

Through centralized monitoring, The University of Chicago will assess the site's performance in the following areas:

- Verification that informed consent was obtained and documented properly
- Adherence to protocol eligibility criteria and requirements
- Conduct and documentation of procedures and assessments related to:
- Study endpoints
- Protocol required safety assessments
- Evaluating, documenting, and reporting unanticipated adverse device effects, subject deaths, and withdrawals, especially when a withdrawal may be related to an adverse event.
- Investigator oversight and delegation of authority to study personnel
- Verification of study-specific required documentation
- Conduct and documentation of procedures essential to trial integrity

As the investigator, the physician is responsible for conducting the study in accordance with the signed agreement, the investigational plan (protocol), applicable laws, FDA regulations, and any conditions of approval imposed by the reviewing IRB/EC. The principal investigator must also accept responsibility for all aspects of the study including the actions of any sub-investigators participating in the study at the investigational site.

#### Data Monitoring

The responsibility of The University of Chicago as sponsor is to ensure protocol and regulatory compliance through proper monitoring of the clinical investigation in U.S. sites. The University of Chicago is also required to ensure that the device is used under the immediate direction of an investigator. As the investigator, the physician is responsible for conducting the clinical investigation in accordance with the signed study agreement, the study protocol, and applicable laws. The primary investigator must also accept responsibility for all aspects of the clinical investigation including the actions of any co-investigators participating in the clinical investigation at the investigational site.

Study data will be reviewed and source verified at The University of Chicago to ensure that the investigator and the clinical investigation team conducts the clinical investigation in accordance with the clinical investigation protocol and applicable FDA and local laws and regulations to ensure adequate protection of the rights, safety and wellbeing of subjects and the quality and integrity of the resulting data.

#### **PATIENT INFORMED CONSENT**

All study subjects must provide written informed consent using the applicable IRB informed consent form. Each patient will receive a copy of his/her signed consent form. The original signed consent document must be kept on file at the investigative site.

The study must be explained in a language that is understandable to the patient and s/he must be allowed sufficient time to decide whether to participate in this study. All subjects will be assured that they have

the right to withdraw from the study at any time during the course of the protocol and this decision will not influence his/her relationship with the lead investigator, the treating physician and/or the study staff.

## **DATA HANDLING, AND RECORD KEEPING, AND CONFIDENTIALITY**

University of Chicago will receive coded study data from participating sites for study analysis.

Data will be collected on paper by study coordinators at the respective participating sites and transcribed into an electronic RedCap database which will be maintained on-campus locations at the University of Chicago. Data will be managed by the PIs and study coordinators. Access to the data will be limited to site PIs and research coordinators only during the study enrollment period.

All patient specific identifiers will be kept separate from the primary research database. The research database will be organized by a unique patient identifier.

## **DEVICE TRACKING**

The Industry-Sponsor may ship investigational devices only to qualified investigators participating in the clinical investigation. A tracking system will be used to maintain complete and accurate record of shipment and disposition of the investigational devices. Records of shipment shall include the name and address of the consignee, type and quantity of device, and date of shipment.

### **Device Tracking By Investigator**

Investigators are responsible for ensuring that investigational devices are made available only to persons who are legally authorized to receive them. Under no circumstances may the investigational device be used/made available to any person who has not been pre-approved by the Sponsor as an investigator for use.

Each site will record lot and model numbers of each device received onto a device tracking log. When a device is used, the subject identification along with the model and lot number of the device used will be recorded. Any device returned to the Industry-Sponsor, due to malfunction, expiration, etc. will also be documented on the device tracking log. Contaminated devices will be returned to Industry-Sponsor in the appropriate biohazard packaging.

Upon completion or termination of a clinical investigation an investigator is required to return to the Industry-Sponsor any remaining supply of devices.

## **FINANCIAL CONSIDERATIONS**

No remuneration will be provided to subjects. Funding for this study will be provided by the industry sponsor: Philips. The industry sponsor will be providing the Visions® PV.035 IVUS catheter and accompanying console to the sites for use in this study.

## Appendix A

### SCHEDULE OF EVENTS

	Screening	Procedure (Day 0)	Pre-discharge
Informed consent	X		
Medical Records Review	X		
Clinical Evaluation	X		
Chest X-ray report	X		
Transesophageal echocardiography (TEE) or Transthoracic echocardiogram	X a		
Transvenous Lead Extraction Data		X	
Venogram results		X	
IVUS images and Fluoroscopy Pictures		X	
Adverse Events	X	X	X

a Discretion of operator

## Appendix B

# Instructions For Use

## Visions® PV .035

DIGITAL IVUS cATHETER

CAUTION – Investigational Device Limited by Federal law to investigational use

English

Page 1

Visions® PV .035

English

DIGITAL IVUS Catheter

## CAUTION:

1. U.S. Federal Law restricts this device to sale by or on the order of a physician.
2. Prior to use, read this entire package insert.

## INTENDED USE:

The Visions® PV .035 catheters are designed for use in the evaluation of vascular morphology in blood vessels of the peripheral vasculature by providing a cross-sectional image of such vessels.

The Visions® PV .035 ultrasound imaging catheters are designed for use as an adjunct to conventional angiographic procedures to provide an image of the vessel lumen and wall structures and dimensional measurements from the image.

## DESCRIPTION:

The Visions PV .035 catheter is an over-the-wire intravascular imaging catheter with a digital ultrasound transducer at the distal end. The transducer utilizes a 64-element cylindrical array that radiates acoustic energy into the surrounding tissue and detects the subsequent echoes. The information from the echoes is used to generate real-time images of the peripheral vessels.

The Visions PV .035 catheter is introduced percutaneously or via surgical cutdown into the vascular system, and is designed to track over 0.035"-0.038" (0.89-0.97mm) guide wires.

The catheter body has markers 1 cm apart along the working length. There are 25 radiopaque markers on the distal end of the catheter, starting 1 cm from the imaging plane, with the 25th RO marker overlapping the distal-most wide inked marker. Inked markers (non-radiopaque) continue along the shaft, spaced 1 cm apart, middle-to-middle, with wider marks indicating 5 cm intervals.

A lubricious GlyDx® hydrophilic coating is applied externally to a distal portion of the catheter.

The Visions PV .035 catheters may only be used with Volcano s5™ Series and CORE™ Series of Systems.

## CONTRAINDICATIONS:

- Use in cerebral vasculature
- Situations presenting a reasonable probability of tissue or organ damage
- Vessel spasm
- Severe calcification
- Angiographic evidence of thrombus
- Severe vessel tortuosity

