## **STUDY DESIGN**

### OVERALL STUDY DESIGN:

This study will be conducted at 4 major institutions (University of Chicago Medicine, Penn Medicine, University of Michigan, Allina Health) that specialize in TLE. The investigators in this study are electrophysiologists with expertise in TLE and imaging using ICE. All adult patients over the age of 21 years scheduled to undergo lead TLE for any indication will be eligible to participate as long as the lead dwell time is greater than 1 year.

Duration of study: 1 year

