## **SUBJECT SELECTION AND WITHDRAWAL**

### SITES:

Subjects selected for study will be recruited from 4 sites: University of Chicago Medicine, Chicago, IL; Penn Medicine, Philadelphia, PA; University of Michigan, Ann Arbor, MI; Allina Health, St.Paul, MN

Eligibility: Patients that have been recommended for lead extraction are eligible for enrollment.

A total of 100 eligible patients will be enrolled in the study. Twenty-five patients will be enrolled at each site which will allow 2 things: (1) the operator will first become comfortable with interpreting the images obtained from IVUS (5 patients) and (2) imaging from the remaining 20 patients will help reinforce understanding of the grading scale [25 patients x 4 sites = 100 patients]. Assuming a Pearson correlation sample size calculation:

- Power: 80%
- Alpha Value: 5%
- Baseline  $H_0$  Correlation: 0.50
- Alternative Correlation: 0.70
- Drop-Out Rate: 20%
- Sample Size Calculation: 100 patients

See Appendix D for further information.

Inclusion:

- Patients at least 21 years of age
- Patients with at least one lead over 1 year dwell time requiring extraction

Exclusion:

- Inability of patient capacity to provide consent for themselves either due to medical or psychiatric comorbidity
- Venous occlusion to the extent that the IVUS catheter cannot pass
- Leads < 1 year dwell time requiring extraction

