## PROCEDURE

Transvenous lead extraction (TLE) should be performed in an EP lab, cardiac OR or hybrid lab as is customary based on the operator's preference. A PA and lateral CXR is recommended any time prior to TLE to confirm the number, type and location of all implanted leads and hardware. The following tests are recommended but left to the discretion of the operator: (1) transesophageal echocardiography (TEE) or transthoracic echocardiogram to look for vegetations (thrombus w/ infection indication) and tricuspid valve (TV) regurgitation, and (2) right or left subclavian vein venogram to evaluate patency of venous structures. If performed, reports of these tests will be collected. Prior to the start of the procedure, the operator will need to perform the following assessment:

1. Assessment of risk and /or difficulty of extraction based on clinical variables alone
  - a. Based on the following clinical variables, what is your assessment of risk or difficulty of extraction? (LOW (L) = 1 point, MODERATE (M) = 2 points, HIGH (H) = 3 points)
 

i. Lead dwell time	LOW	MODERATE	HIGH
ii. Number of leads in vascular space	LOW	MODERATE	HIGH

iii. Type of lead	LOW	MODERATE	HIGH
iv. BMI of patient	LOW	MODERATE	HIGH
v. Patient age	LOW	MODERATE	HIGH
vi. Gender (male=1 point, female=2 points)			

TOTAL: 6-8 points = overall LOW risk , 9-11 = MODERATE risk, 12-17 = HIGH risk

- b. Are you planning on inserting the Philips Rescue Balloon guidewire (PRB-G) during this case?
  - i. If Yes, why?
  - ii. If No, why not?
  - iii. If you are going to use the PRB-G, are you planning on inserting the Rescue Balloon up front? YES or NO

Two or more large (7F – 12F) venous sheaths will be inserted in the right and left femoral veins as per standard of care as part of the TLE procedure. A 8.5F SRO or other long sheath can help direct the IVUS (Visions® PV.035) catheter and may be used as one of the two standard of care access sheaths. If a long sheath is not used, an 8.5 F short sheath is the minimum size required to use the IVUS catheter.

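### A patient whose vein the catheter can pass, but who has angiographic thrombus, severe calcification or severe tortuosity, is eligible under the protocol body and contraindicated under its own Appendix B

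*Combined protocol and SAP*

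**What the plan says.** Eligibility appears in two places. Overall Study Design admits adults over 21 having extraction "for any indication will be eligible to participate as long as the lead dwell time is greater than 1 year". The list under Subject Selection and Withdrawal has three exclusions. One concerns patients who cannot consent for themselves, and another concerns leads implanted for less than a year. The remaining one is the only one about the veins: "Venous occlusion to the extent that the IVUS catheter cannot pass".

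The Procedure section then has the catheter introduced from a femoral vein before the pocket is opened, and attaches no condition about the state of the vein. Echocardiography and a subclavian venogram are recommended but left to the operator. The venogram's stated purpose is to assess patency. The Schedule of Events (Appendix A) places venogram results at the procedure, Day 0.

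Appendix B, the device instructions, lists six contraindications. Three describe findings in the patient's vessels that could be present before the catheter goes in: "Angiographic evidence of thrombus", "Severe calcification" and severe vessel tortuosity.

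**The concern.** The protocol body and its appendix answer the same question differently for some patients. Under the body, what matters about the vein is whether the catheter can get through. Under the appendix, certain findings count against using the catheter even when it can get through.

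Two things are at stake. The first is patient safety: the catheter is used for research imaging, and Appendix B names embolism, perforation and vessel injury among its possible adverse effects. The second is interpretation of the results. The primary endpoint is whether IVUS can image lead adherence. If an operator sees a listed finding and withholds the catheter, the protocol does not say whether that patient is ineligible, an imaging failure or a dropout. If the operator proceeds, nothing marks the patient for separate inspection in the safety results.

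**Working it through.** The plan states no figure on this point, so the check compares texts.

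**Step 1: sort the six contraindications.** Use in the cerebral vasculature and vessel spasm are conditions of use and would not normally be enrolment criteria. The clause on a reasonable probability of tissue or organ damage is a general judgement. That leaves three specific findings: angiographic thrombus, severe calcification and severe tortuosity.

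**Step 2: match them to the three exclusions.**

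| Finding in Appendix B | Covered by consent capacity? | Covered by occlusion? | Covered by dwell time? |
|---|---|---|---|
| Angiographic thrombus | No | Only if the catheter cannot pass | No |
| Severe calcification | No | Only if the catheter cannot pass | No |
| Severe tortuosity | No | No | No |

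None of the three findings is named as an exclusion. The occlusion criterion tests passability, so it leaves in every patient whose vein is affected but passable.

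**Step 3: look for text elsewhere that closes the gap.**

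- *Procedure section.* Insertion is unconditional, and no echo or venogram result is tied to exclusion or to withholding the catheter.
- *Calcification.* The only item in the body concerns the device pocket. It is descriptive and is noted after the first imaging run.
- *Risks section.* It sends the reader to the instructions for use for potential risks and does not adopt the contraindications.
- *Background and Rationale.* It acknowledges off-label use, but for the route through the right atrium. The contraindications are not discussed.
- *Study Device.* It cites Appendix B without comment.
- *Appendix B itself.* It tells the user to read the whole insert. That informs the operator but sets no eligibility rule.

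**Step 4: timing.** Thrombus is contraindicated on angiographic evidence, and the only angiographic test mentioned before imaging is the venogram. It is optional and its result is scheduled for Day 0, whereas consent and screening come earlier. A finding can therefore appear in a patient already enrolled, and the section headed selection and withdrawal has no rule for that case.

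**Step 5: reach.** Enrolment is 100, from 80 evaluable and 20% dropout: 80 / (1 − 0.20) = 100. Each affected patient is 1/100, or 1 percentage point, of those enrolled. How many there will be cannot be worked out from the documents. Appendix D defines dropouts as patients lost at random. A catheter withheld because of a vessel finding would not obviously fit that definition.

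**The case against.** The strongest reply is that this is silence in one place and not two conflicting orders. The exclusion list governs enrolment, the instructions govern use of the device, and the instructions are part of the protocol package. An operator can comply with both by enrolling the patient and then not inserting the catheter. Much of this stands. A reader might infer that the protocol tells operators to image despite a contraindication, and no passage says so. What remains is that the body's only vein-related test is passability and its insertion step is unconditional, so an operator who proceeds has also followed the body as written.

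Other tempting readings go too far:

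- *Every extraction patient is eligible.* Age, dwell time and three exclusions apply.
- *The protocol expects contraindicated thrombus because echo is used "to look for vegetations (thrombus w/ infection indication".* That phrase concerns echocardiography. Appendix B speaks of angiographic evidence, so an echo finding is not literally the listed one.
- *The non-significant-risk argument depends on the label.* It cites published literature and the sponsor's own 56 patients. It does not, however, say whether those patients had any of the listed findings.
- *Severe vessel calcification is common here.* Nothing in the documents shows that.

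It is also fair to note that existing safeguards help. Echo and venogram reports are collected when done, IVUS complications are recorded, and a physician outside the study adjudicates potential IVUS-related events. These act after use and do not settle who should be imaged.

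**Conclusion.** The inconsistency is real and should be resolved. For a passable vein with angiographic thrombus, severe calcification or severe tortuosity, the protocol body permits enrolment and catheter use, the appendix contraindicates use, and no other passage settles the difference. The conclusion rests on the text alone.

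Its size is unknown. The documents give no frequency for any of the three findings, and a percentage of the 100 patients would be a guess. They show that such patients can be enrolled, not that they will be. A reader might also infer that the study population will differ from site to site according to venogram practice. That is possible, but since no venogram result is tied to eligibility, the documents do not establish it. The sample-size calculation and the planned correlations are unaffected.

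**What to change.** The sponsor should reconcile the exclusion list and the insertion step in the Procedure section with the contraindications in Appendix B. Either the applicable contraindications are carried into eligibility and device use, or each departure is stated and justified, as the protocol already does for the off-label route. Which clinical rule applies is for the sponsor and investigators; this review does not choose one.

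Whichever is chosen, add a line to the procedure-day form, and to the screening form where the information is already known, recording which listed findings are present and whether the catheter was withheld. A screening-only line would miss venogram findings. State how a patient whose catheter was withheld counts in the imaging endpoint, and identify patients with a listed finding in the safety and imaging-success results.

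The cost is some eligibility and procedure wording and one checklist line. A few patients may become ineligible.
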